## HBI-8000-210 Protocol Synopsis

Name of Sponsor/Company:	HUYA Bioscience International, LLC		
Study Drug:	HBI-8000		
Title of Study:	A Phase 2b Open-Label Single-Arm Study to Evaluate the Efficacy and Safety of Oral HBI-8000 in Patients with Relapsed or Refractory Adult T-Cell Lymphoma(ATL)		
Protocol No:	HBI-8000-210		
Study site(s):	25 to 35 sites in Japan		
Study duration: Approximately 36 months	Phase: 2b		
Planned study period: 4Q 2016 (first patient in) to 4Q 2018 (last patient in) 4Q 2019 study completion			
Objectives:			
Primary:	
 
To determine the efficacy of HBI-8000 administered twice a week (BIW) continuously
 
		
Secondary:	
 
To evaluate the safety and tolerability of HBI-8000 administered twice a week (BIW) continuously
 
		
Endpoints:			
Primary:	
 
Objective response rate (ORR; Complete Response [CR] + Unconfirmed CR [CRu] + Partial Response [PR])
 
		
Secondary:	
 
ORR by disease subtype (see inclusion criteria)
 
Median duration of progression-free survival (PFS)
 
Median duration of response (DOR)
 
Safety
 
		
Exploratory:	
 
Median duration of overall survival (OS)
 
		
Study Design:	
This is a Phase 2b, open-label, non-randomized, single-arm study to evaluate the safety and efficacy of HBI-8000 40 mg BIW in patients with relapsed or refractory ATL (R/R ATL). HBI-8000 will be administered orally approximately 30 minutes after any regular meal. The treatment will be continuous, with 3 to 4 days between dosing. A cycle is defined as 28 days solely for the purpose to schedule assessments required by the study.
 
Treatment-related adverse events (AEs) will be graded according to National Cancer Institute Common Terminology Criteria for Adverse Events (NCI CTCAE) version 4.03. In the event of unacceptable toxicities, study drug will be held until recovery and dosing will be resumed at reduced dose level, following protocol guidelines. An unacceptable toxicity is defined as the following:
 
 
Grade 4 afebrile neutropenia >7 days despite optimal growth factor support
 
Grade <math>\geq 3</math> febrile neutropenia or neutropenic infection
 
Grade <math>\geq 3</math> thrombocytopenia with clinically significant bleeding or Grade <math>\geq 3</math> thrombocytopenia requiring a platelet transfusion
 
Grade <math>\geq 3</math> nausea, vomiting, diarrhea, or electrolyte imbalances lasting greater than 48 hours despite optimal prophylactic and curative treatment
 
		

- Grade  $\geq 3$  allergic reaction
- Grade  $\geq 3$  other non-hematologic AEs
- Treatment delay  $> 14$  days secondary to recovery from study drugs-related AEs

For determination of efficacy, HBI-8000 administration will be continued until disease progression or unacceptable toxicities are observed despite appropriate dose reduction or treatment interruption.

Number of patients:	Eighteen Japanese patients with relapsed or refractory ATL evaluable for efficacy. To ensure meeting this target, an estimated 22 patients would be enrolled in anticipation that some patients may not complete study treatment.
Entry Criteria:	
Inclusion
 
 
1. Histopathological or cytological diagnosis of ATL confirmed as seropositive for anti-Human T-lymphotrophic Virus type-I (HTLV-1) antibody
 
2. Acute, lymphoma or unfavorable chronic types. The unfavorable chronic type is defined by the presence of at least 1 of the following: serum albumin <math>< 3.5</math> g/dL, lactic dehydrogenase (LDH) <math>> 300</math> U/L, or blood urea nitrogen (BUN) <math>> 25</math> mg/dL. The patient must have at least 1 of measurable lesion, or evaluable lesion in either of peripheral blood or skin
 
3. Relapsed or refractory disease after receiving prior systemic therapy with mogamulizumab, or <math>\geq 1</math> prior systemic therapy with cytotoxic chemotherapy in case of intolerance/contraindication for mogamulizumab. And there is no other standard treatment which can be considered appropriate for patients
 
4. Male or female, aged 20 years or older
 
5. Eastern Cooperative Oncology Group (ECOG) Performance Status of 0 to 2
 
6. Life expectancy of greater than 3 months
 
7. Meeting the following baseline laboratory criteria for screening: 
 
a. Absolute Neutrophil Count <math>> 1500/\mu\text{L}</math> independent of growth factor support within 7 days
 
b. Platelets <math>> 75,000/\mu\text{L}</math> independent of transfusion within 14 days
 
c. Hemoglobin <math>> 8\text{ g/dL}</math> independent of transfusion within 14 days
 
d. Serum creatinine <math>< 1.5 \times</math>upper limit of normal (ULN)
 
e. Serum aspartate aminotransferase/glutamyl oxaloacetic transaminase (AST/SGOT) and alanine aminotransferase/glutamyl pyruvic transaminase (ALT/SGPT) <math>\leq 3 \times</math>ULN
 
f. Serum bilirubin <math>\leq 1.5 \times</math>ULN
 
 
 
8. Negative serum pregnancy test for females of childbearing (reproductive) potential. Female patients of child bearing potential must use an effective method of birth control (e.g., hormonal contraceptive, intrauterine device, diaphragm with spermicide or condom with spermicide) during treatment period and 1 month thereafter. Males must use an effective method of birth control (2 barrier methods) during treatment period and 3 months thereafter. Note: Female patients will be considered to be women of childbearing potential unless having undergone permanent contraception or postmenopausal. Postmenopausal is defined as
 


	
at least 12 months without menses with no other medical reasons (e.g., chemical menopause because of treatment with anti-cancer agents)
 
9. Signed informed consent
 
Exclusion
 
 
1. Patients in whom central nervous system lymphoma is recognized during screening (if suspected clinically, imaging study should be performed to confirm)
 
2. Male patients with QTcF >450 msec at screening, female patients with QTcF >470 msec at screening, or patients with congenital long QT syndrome, clinically significant arrhythmia, history of congestive heart failure (New York Heart Association Class III or IV), or acute myocardial infarction within 6 months of starting the study drug
 
3. Patients with known hypersensitivity to benzamide class of compounds or any of the components of HBI-8000 tablets, and patients with prior exposure of HBI-8000
 
4. Patients with a history of second malignancy other than disease under study. The exceptions are diseases (excluding diseases listed below) that have been treated with curative intent with no evidence of recurrence in past 5 years. Furthermore, if the second malignancy is one of the following diseases that were treated with curative intent, it is only required that there is no evidence of recurrence in past 2 years: 
 
a. Basal cell carcinoma of the skin
 
b. Squamous cell carcinoma of the skin
 
c. Cervical carcinoma in situ
 
d. Carcinoma in situ of the breast
 
e. An incidental histological finding of prostate carcinoma (TNM stage T1a or T1b)
 
f. Early stage gastric cancer treated with endoscopic mucosal resection or endoscopic submucosal dissection
 
 
 
5. Autologous stem cell transplantation within 12 weeks (84 days) of starting the study drug
 
6. History of allogeneic stem cell transplantation
 
7. Organ transplantation recipients except autologous hematopoietic stem cell transplantation
 
8. Uncontrolled intercurrent infection
 
9. Hepatitis B surface antigen-positive, or hepatitis C virus antibody positive. In case hepatitis B core antibody and/or hepatitis B surface antibody is positive even if hepatitis B surface antigen-negative, a hepatitis B virus deoxyribonucleic acid (DNA) test (real-time polymerase chain reaction [PCR] measurement) should be performed and if positive, the patient should be excluded from study
 
10. Any history of testing positive for human immunodeficiency virus or known acquired immunodeficiency syndrome
 
11. Uncontrolled diabetes mellitus, hypertension, endocrine disorder, bleeding disorder
 
12. Major surgery or radiation therapy within 28 days of starting the study drug
 
13. Receiving investigational agents or anti-cancer therapy within
 

--	--

	
28 days, nitrosourea or mitomycin C within 42 days of starting the study drug
 
14. Receiving antibody therapy for ATL within 4 weeks of starting the study drug
 
15. Women who are breastfeeding or women who are not willing to stop breastfeeding during study treatment period and for 30 days after the last dose of study drug
 
16. Potential for non-compliance or at increased risk based on investigator's judgement

Excluded Prior or Concomitant Medications or Therapy:	
The following drugs are prohibited:
 
 
 Drugs known to produce significant QT prolongation and ventricular dysrhythmias (see Appendix E)
 
 
Prohibited from signing informed consent through the end of treatment (EoT) assessment
 
 
 Anti-cancer therapy other than study medication
 
 
Prohibited during the study and within the following time intervals prior to the first dose of study drug;
 
 
- 4 weeks for anti-cancer chemotherapy
 
- 6 weeks for nitrosourea or mitomycin C
 
- 4 weeks for anti-cancer monoclonal antibody therapy
 
 
Corticosteroids prescribed for medical conditions other than lymphoma is not considered as anti-cancer therapy for this study, for example: chronic obstructive pulmonary disease, allergy, topical steroids for rash.

Treatments:	Study drug is to be taken after any regular meal twice weekly, each dose separated by 3 to 4 days. Treatment will continue until PD in the absence of unacceptable toxicity.
Efficacy Data:	Response and progression for ATL will be evaluated according to the criteria of the International Consensus Meeting [ Tsukasaki 2009 ] (modified).
Safety Data:	
All patients who receive at least 1 dose of HBI-8000 will be evaluable for safety. AE severity (Grade) will be defined according to Common Terminology Criteria for Adverse Events (CTCAE) Version 4.03. Serial electrocardiograms (ECGs) and clinical laboratory tests will be collected to evaluate safety and potential toxicity. Laboratory and other tests, as appropriate to the clinical situation, may be obtained more frequently than stipulated in the schedule of events.
 
All reported AEs will be collected, evaluated, and coded using Medical Dictionary for Regulatory Activities (MedDRA).

Statistical Procedures:	

Statistical analysis for all safety and efficacy parameters will be primarily descriptive in nature. Categorical variables will be summarized by frequency distributions (number and percentages of patients), continuous variables will be summarized by mean, standard deviation, median, minimum, and maximum, and time-to-event variables will be summarized using Kaplan-Meier methods and figures for the estimated median time. A formal statistical analysis plan will be completed prior to database lock and any study-related analyses.
 
Efficacy should be analyzed by Full analysis set (FAS) and Per protocol set (PPS). The FAS is defined as Patients meeting all eligibility criteria and having received at least one dose of study medication, and at least one efficacy assessment of disease with either imaging studies or clinical examination after receiving study medication.
	

The PPS is defined as Patients meeting all eligibility criteria and having completed Cycle 1 treatment or discontinued study treatment during cycle 1 due to clinical PD. It should be noted that the PPS includes subjects who discontinue within Cycle 1 due to clinical PD without imaging studies to assess disease status. For efficacy determination, 18 patients evaluable for efficacy per protocol criteria are required. To ensure meeting this target, 22 patients would be enrolled if 20% of patients are assumed not to complete required study treatment or evaluations for efficacy determination. Enrolled patients will be treated with the starting dose of 40 mg BIW to provide an assessment of tumor response as well as additional safety data.

The target best ORR for this study is 30%, on the basis of the ORR results that were obtained in study TG0902CDM. The power for showing the response rate  $>5\%$  at 5% two-sided alpha in 18 patients is 80%.

Any patient that has received any amount of study medication will be considered as evaluable for safety. Safety data will be summarized with descriptive statistics and frequency tables and will include AEs, hematology, coagulation, serum chemistry, urinalysis, vital signs, and ECG data. Laboratory values will be summarized by numerical value and toxicity grade.

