### **2.6.8 Management and Dosage Modifications for Unacceptable Hematologic and Non-hematologic Adverse Events**

National Cancer Institute Common Terminology Criteria for Adverse Events (NCI CTCAE) version 4.03 will be used to grade the severity of toxicities. An unacceptable toxicity is defined as the following treatment-related AEs:

- Grade 4 afebrile neutropenia >7 days despite optimal growth factor support
- Grade  $\geq 3$  febrile neutropenia or neutropenic infection
- Grade  $\geq 3$  thrombocytopenia with clinically significant bleeding or Grade  $\geq 3$  thrombocytopenia requiring a platelet transfusion
- Grade  $\geq 3$  nausea, vomiting, diarrhea, or electrolyte imbalances lasting greater than 48 hours despite optimal prophylactic and curative treatment
- Grade  $\geq 3$  allergic reaction
- Grade  $\geq 3$  other non-hematologic AEs
- Treatment delay >14 days secondary to recovery from study drugs- related AEs

**Table 1** summarizes the guidelines for dosage adjustment in the event of unacceptable AEs. Two dose reductions are allowed (from 40 mg to 30mg, or from 30 mg to 20 mg). If unacceptable AEs recur despite 2 dose reductions, the study treatment will be permanently discontinued and post-treatment follow-up ensues. However, if the patients are having clinical benefit, further treatment may be considered after discussion with the sponsor. In the event of AE, such as hematological AE-uncomplicated, necessitating 2 treatment interruptions, dose will be reduced when treatment resumes. However, if strongly needed for patient safety, dose can be reduced according to the investigator judgement, even if unacceptable hematological AE-uncomplicated is occurred once.

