**Table 1: HBI-8000 Tablet Dosage Adjustment Guidelines**

AE Category	AE Description	Dosage interruption with/without Reduction
Hematological Adverse Events-- Uncomplicated	

• Neutropenia Grade 3 or 4 upon observation

• Thrombocytopenia Grade 3 or 4 upon observation

	Hold dose, initiate G-CSF, once resolved to $\leq 1$ within 2 weeks, resume at same dose.  Hold dose, once resolved to $\leq 1$ within 2 weeks, resume at same dose.  If recovery takes $>2$ weeks, discontinue study drug.
Hematological Adverse Events-- Complicated	

• Grade 4 afebrile neutropenia <math>> 7</math> days despite optimal growth factor support

• Grade <math>\geq 3</math> febrile neutropenia or neutropenic infection

• Grade <math>\geq 3</math> thrombocytopenia with clinically significant bleeding or Grade <math>\geq 3</math> thrombocytopenia requiring a platelet transfusion

	Hold doses, once resolved to $\leq 1$ within 2 weeks, resume at reduced dose (from 40 mg to 30 mg, or from 30 mg to 20 mg);  If recovery takes $> 2$ weeks, discontinue study drug.
Non-Hematological Adverse Events (excluding laboratory values without clinical significance)	Grade 3	Hold doses, once resolved to $\leq 1$ within 2 weeks, resume at reduced dose (from 40 mg to 30 mg, or from 30 mg to 20 mg), with appropriate prophylaxis as applicable.  If recovery takes $>2$ weeks, discontinue study drug.
	Grade 4	Discontinue study drug

The G-CSF is recommended to be prescribed when uncomplicated Grade 3 or 4 neutropenia is observed. Patient management should follow institution guidelines and be recorded in eCRFs. Laboratory tests should be obtained at least once a week to monitor recovery.

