## **2.6.9 Management and Dosage Modifications for Non-Hematologic Adverse Events**

In the event of Grade 3 non-hematologic AEs (excluding isolated abnormality of laboratory values not associated with clinical significance), study medication should be held. Appropriate treatment should be initiated. Patients will be closely monitored for recovery and managed following the Dose Adjustment Guideline. If the AEs recur despite 2 dose reductions as applicable, study treatment should be discontinued. Study treatment should be terminated if Grade 4 non-hematologic adverse events occur, following the Dose Adjustment Guideline (Table 1).

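### For a treatment delay over 14 days and for clinically significant Grade 4 non-hematologic events, the synopsis says resume at a reduced dose while Table 1 says discontinue

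*Combined protocol and SAP*

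**What the plan says.** **Synopsis, Study Design.** For unacceptable toxicities, "study drug will be held until recovery and dosing will be resumed at reduced dose level, following protocol guidelines". The list that follows includes Grade 3 or higher "other non-hematologic AEs", with no separate treatment of Grade 4, and a delay of more than 14 "days secondary to recovery from study drugs-related AEs".

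**Section 2.6.8.** It repeats the list, including "Treatment delay >14 days secondary to recovery from study drugs- related AEs", and refers to Table 1 for dose adjustment. Its prose allows two dose reductions and makes discontinuation permanent if unacceptable events recur after both. It then adds that patients who are benefiting may be considered for further treatment once this has been discussed with the sponsor.

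**Table 1.** In every category where the dose is held, recovery taking more than 2 weeks leads to the instruction "discontinue study drug". Grade 4 non-hematologic events also lead to discontinuation. The non-hematologic category leaves out laboratory values without clinical significance.

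**Section 2.6.9.** "Study treatment should be terminated if Grade 4 non-hematologic adverse events occur, following the Dose Adjustment Guideline".

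**The concern.** Two situations have opposite instructions in the current text. A reader of the synopsis would expect the patient to go back on drug at a lower dose; a reader of Table 1 would stop treatment. Whether a patient is exposed again after serious toxicity should not depend on which page is consulted.

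The trial plans 25 to 35 sites for about 22 patients, which is fewer than one patient per site on average (22/25 = 0.88; 22/35 = 0.63). A difference in reading between sites would therefore show up as a difference in treatment between individual patients, and could not be examined as a site effect. It would feed into the count of discontinuations, into dose intensity (Section 5.8) and, for events in Cycle 1, into who belongs to the PPS (Section 5.5.2).

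**Working it through.** No figure in the plan needs reproducing. The check is to follow each situation through the four places. The only conversion is 2 weeks = 14 days, so the time thresholds in the list and in Table 1 are identical.

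| Situation | Synopsis | Section 2.6.8 prose | Table 1 | Section 2.6.9 |
|---|---|---|---|---|
| Delay over 14 days for recovery from a drug-related event | Hold, then resume reduced | On the list; permanent stop tied to recurrence after two reductions | Discontinue | Not addressed directly; refers to Table 1 |
| Grade 4 non-hematologic event, clinically significant | Hold, then resume reduced | On the list as Grade 3 or higher; same stopping text | Discontinue | Terminate |
| Grade 3 non-hematologic or complicated hematologic event, recovered within 2 weeks | Hold, then resume reduced | On the list; two reductions allowed | Resume reduced | Hold, then Table 1 (non-hematologic) |

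The third row shows no conflict. The disagreement is confined to the first two rows. In the second it is limited to clinically significant events, because Table 1 excludes other laboratory values while the synopsis list carries no such exclusion.

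**Section 2.6.8 does not settle the matter.** Its prose links permanent discontinuation to recurrence after two reductions, while its own table stops treatment at once in both situations. The sponsor-discussion exception follows the sentence on recurrence. Whether it also covers the immediate stops in Table 1 is not stated.

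**Effect on the PPS.** Section 5.5.2 requires completion of Cycle 1 treatment, or discontinuation during Cycle 1 because of clinical progression. Take an eligible patient with a clinically significant Grade 4 non-hematologic event in Cycle 1:

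- Stopped under Table 1: Cycle 1 is not completed and the reason is not progression, so the patient is outside the PPS.
- Resumed under the synopsis and Cycle 1 completed: the patient is inside the PPS.

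Sections 2.6.6 and 5.4 do not replace patients who withdraw in Cycle 1 because of drug toxicity. Such a loss is absorbed only by the margin between 22 enrolled and 18 evaluable, which is 22 − 18 = 4 patients. The planned numbers and the power statement in Section 5.2 do not change.

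**The case against.** The best defence is the cross-referencing. The synopsis sentence ends by deferring to protocol guidelines. Section 2.4.1, which says only that drug may be held and dose may be reduced, sends the reader to Section 2.6.8 for those guidelines, and Section 2.6.8 sends the reader to Table 1. Table 1 and Section 2.6.9 agree on Grade 4. No body section says to resume in either situation; that instruction sits in one summary sentence. The synopsis also says that dosing ends when unacceptable toxicity persists despite reduction or interruption, and Sections 2.6 and 2.6.6 treat such toxicity as a reason to stop.

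Much of this stands. A site that follows the chain would reach Table 1, so the text supports only that sites *could* diverge, not that they would. It does not remove the conflict. The synopsis sentence states resumption outright for a list that contains both situations, and the prose of Section 2.6.8 leaves the exception's reach open.

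The defence also rightly limits the effect on efficacy. Stopping drug does not end assessment. Patients who stop before progression have a tumor assessment at the end-of-treatment visit if the last was more than 30 days earlier, then about every 3 months until progression or new therapy (Section 2.6.4). A response already recorded still counts. Discontinuation after Cycle 1 does not remove a patient from the PPS, and the full analysis set needs only one post-dose assessment in an eligible, treated patient.

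**Conclusion.** The inconsistency is real and should be corrected. It concerns two situations: a delay of more than 14 days for recovery from drug-related events, and a clinically significant Grade 4 non-hematologic event. The consequences are for patient safety, discontinuation counts, dose intensity and, in Cycle 1, PPS membership. No view is taken on which rule is right.

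Its size in patients cannot be given. A reader might apply the Phase 1 experience in Section 1.8, where 2 of 6 patients at 40 mg had Grade 3 or 4 toxicity, and infer 22 × 2/6 = 7.3, or about 7 patients. The documents do not support that. One of the two events was a Grade 4 neutropenia that resolved promptly with growth factor. The other was a Grade 3 ALT elevation that resolved with interruption, with no recovery time stated. Neither is a Grade 4 non-hematologic event, and neither is shown to have caused a delay of more than 14 days.

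A reader might also infer that one patient stopped or continued under the wrong rule could decide the primary result, since response counts in 18 patients are small. The documents show no route by which this wording would change an individual's recorded response, and assessment continues after treatment stops. The supported effect on efficacy is the narrower one on Cycle 1 PPS membership.

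The conclusion rests on the wording alone, and on reading Grade 3 or higher as including Grade 4.

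**What to change.** Reconcile the synopsis (Study Design), Section 2.6.8, Table 1 and Section 2.6.9 so that a delay of more than 14 days and a clinically significant Grade 4 non-hematologic event each have one stated consequence, worded identically in all four places. Carry the exclusion of laboratory values without clinical significance consistently. State whether the sponsor-discussion exception in Section 2.6.8 applies to the Table 1 stops. Which consequence applies is the sponsor's clinical decision.

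The cost is wording in a protocol amendment and a notice to sites. No change to the sample size or the analysis is needed.
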